5. TEST ARTICLE ALLOCATION AND MASKING

5.1. Test Article Allocation

The study lenses will be worn in a bilateral and random fashion using a 2×2 crossover design. A computer-generated randomization scheme will be used to randomly assign subjects to one of the two possible lens wear sequences (-1.00/-1.75 or -1.75/-1.00 DC) within each refraction and toric fit type group. See Table 1 below for additional details regarding the randomization for this study. The random scheme will be generated using the PROC PLAN procedure from Statistical Analysis System (SAS) Software Version 9.4 or higher (SAS Institute, Cary, NC).¹⁰

Randomization will be performed prior to the first lens fitting. The following must have occurred prior to randomization:

- Informed consent must have been obtained.
- The subject must have met all eligibility criteria.
- The subject's screening and baseline information must have been collected.

Clinical Study Protocol

Johnson & Johnson Vision Care, Inc.

Table 1 Randomization Scheme for 2x2 Crossover by Refraction Group and Toric Fit Type

Refractive Error Group	Toric Fit Type	Sequence	Period 1	Period 2
Myope (-3.00 DS)	against-the-rule astigmatism (90° axis)	1	-1.00 DC	-1.75 DC
		2	-1.75 DC	-1.00 DC
	with-the-rule astigmatism (180° axis)	1	-1.00 DC	-1.75 DC
		2	-1.75 DC	-1.00 DC
Hyperope (+3.00 DS)	against-the-rule astigmatism (90° axis)	1	-1.00 DC	-1.75 DC
		2	-1.75 DC	-1.00 DC
	with-the-rule astigmatism (180° axis)	1	-1.00 DC	-1.75 DC
		2	-1.75 DC	-1.00 DC

5.2. Masking

Subjects will be unaware (masked) of the identity and differences between the investigational products to help reduce potential bias. Investigators and clinical site personnel involved in the data collection will not be masked as to the identity of the investigational product.

5.3. Procedures for Maintaining and Breaking the Masking

Investigators and site personnel will not be masked to the identity of the investigational lenses; therefore, these procedures are not applicable.

6. STUDY INTERVENTION

6.1. Identity of Test Articles

The following contact lenses will be used in this study:

Table 2: Test Articles

Name	Test Lens
	JJVC Investigational Multifocal Toric Contact Lenses manufactured in Senofilcon A (C3) material with UV/HEV filter

Clinical Study Protocol

Johnson & Johnson Vision Care, Inc.

	Test Lens
Manufacturer	JJVC
Lens Material	senofilcon A(C3) with chromophore
Nominal Base Curve	8.5
Nominal Diameter	14.3
Nominal Distance Powers (D)	-3.00, +3.00
Nominal Cylinder Powers (D)	-1.00, -1.75
Cylinder axes (°)	90, 180
Nominal ADD Power (D)	Mid
Water Content	38%
Oxygen Permeability (Dk)	122.0
Wear Schedule in Current Study	Daily Disposable
Replacement Frequency	Daily
Packaging Form (vial, blister, etc.)	Blister

Each subject will wear 4 lenses in this non-dispensing study, plus any additional lenses needed for replacements.

6.2. Ancillary Supplies/Products

The following solutions will be used in this study:

Table 3: Ancillary Supplies

	Single-Use Preservative-Free Rewetting Solutions (any of these three options may be supplied)		
Solution Name/Description	Eye-Cept® Rewetting Drops	ScleralFil® Preservative Free Saline Solution	LaciPure Saline Solution
Manufacturer	Optics Laboratory	Bausch + Lomb	Menicon
Preservative	Non-Preserved	Non-Preserved	Non-Preserved

Stopwatches will be provided to research sites to help with managing the timing of toric fit assessments and lens settling.

6.3. Administration of Test Articles

[figure not shown]
Test articles will be dispensed to subjects meeting all eligibility requirements, including any dispensing requirements set forth in this clinical protocol. Test articles which are lost or damaged may be replaced at the discretion of the Investigator.

Clinical Study Protocol

Johnson & Johnson Vision Care, Inc.

6.4. Packaging and Labeling

The test articles will be packaged in blisters as the primary packaging with an investigational lens label. The test articles will be in plastic bags as the secondary packaging form. The sample study label is shown below:

6.5. Storage Conditions

Test articles will be maintained at ambient temperatures at the clinical site. Test articles must be kept under secure conditions.

6.6. Collection and Storage of Samples

When possible, any lens or test article associated with an Adverse Event and/or a Product Quality Complaint must be retained and stored in a glass vial with moderate solution pending directions from the sponsor for potential return to JJVC.

6.7. Accountability of Test Articles

JJVC will provide the Investigator with sufficient quantities of study articles and supplies to complete the investigation. The Investigator is asked to retain all lens shipment documentation for the test article accountability records.

Test articles must be kept in a locked storage cabinet, accessible only to those assigned by the Investigator for dispensing. The Investigator may delegate this activity to authorized study site personnel listed on the Site Delegation Log. All test articles must be accounted. This includes:

1. What was dispensed for the subject for trial fitting
2. The number and reason for unplanned replacements.

Following final reconciliation of test articles by the monitor, the Investigator or monitor will return all unused test articles to JJVC.

Clinical Study Protocol

Johnson & Johnson Vision Care, Inc.

If there is a discrepancy between the shipment documents and the contents, contact the study monitor immediately.

7. STUDY EVALUATIONS

7.1. Time and Event Schedule

Table 4: Time and Events

Visit Information	Visit 1 Screening, Baseline, Treatment 1 and 2
Time Point	Day 0
Estimated Visit Duration	2.5 hours
Statement of Informed Consent	X
Demographics	X
Medical History and Concomitant Medications	X
Habitual Contact Lens Information	X
Habitual Contact Lens Wear Schedule	X
Contact Lens History	X
Eligibility after Screening	X
Ocular Symptoms	X
Entrance Distance Visual Acuity	X
Keratometry / SimK	X
Subjective Sphero-cylindrical Refraction	X
Refraction Type	X
Biomicroscopy	X
Eligibility at Baseline	X
Instructions	X
Randomization	X
Lens Selection	XX
Right Lens Insertion	XX
Timed Settling for Right Lens	XX
Left Lens Insertion	XX
Timed Settling for Left Lens	XX
Toric Fit Evaluation (7, 15, 25 minutes)	XX
Lens Fit Assessment	XX
PRO questionnaire	XX
Lens removal	XX
Biomicroscopy	X
Washout period	X
Final Evaluation	X

Note: X = performed once, XX = performed twice.

Clinical Study Protocol

Johnson & Johnson Vision Care, Inc.

7.2. Detailed Study Procedures

VISIT 1

The subjects must present to Visit 1 wearing spectacles with distance vision correction, having not worn contact lenses on the day of the visit.

Visit 1: Screening		
Step	Procedure	Details
1.1	Statement of Informed Consent	
Each subject must read, understand, and sign the Statement of Informed Consent before being enrolled into the study. The Principal Investigator or his/her designee conducting the informed consent discussion must also sign the consent form.
 
Note: The subject must be provided a signed copy of this document.

1.2	Demographics	Record the subject's year of birth, age, gender, race and ethnicity.
1.3	Medical History and Concomitant Medications	Questions regarding the subject's medical history and concomitant medications.
1.4	Habitual Contact Lens Information	Questions regarding the subject's habitual lens type and parameters.
1.5	Habitual Contact Lens Wear Schedule	
Record the duration of wearing this contact lens type and power (number of years and months).
 
During the past four weeks, what is the minimum number of days per week that the subject has worn their lenses for at least 8 hours.

1.6	Contact Lens History	Record the subject's correction type (i.e. monovision, multifocal, sphere with readers, etc.).
1.7	Eligibility after Screening	
All responses to Screening Inclusion Criteria questions must be answered "yes" and all responses to Exclusion Criteria must be answered "no" for the subject to be considered eligible.
 
If subject is deemed to be ineligible after screening, proceed to Final Evaluation and complete Subject Disposition. Refraction and Biomicroscopy forms are not required.

Clinical Study Protocol
Johnson & Johnson Vision Care, Inc.

Visit 1: Baseline		
Step	Procedure	Details
1.8	Ocular Symptoms	Subjects will respond to a verbal open-ended symptoms questionnaire.
1.9	Entrance Distance Visual Acuity	Record the distance Snellen visual acuity (OD, OS, OU) to the nearest letter with the subject's habitual distance spectacle correction in place.
1.10	Keratometry / SimK	Keratometry/SimK will be performed OD and OS and the steep and flat dioptric power and corresponding meridians recorded.
1.11	Subjective Sphero-cylindrical Refraction	An optimal, binocular balanced distance sphero-cylindrical refraction will be performed. Record the refraction and distance visual acuity (OD, OS, OU) to the nearest letter. Note: Best distance visual acuity with sphero-cylindrical refraction must be at least 20/25 in each eye for the subject to be eligible for the study.
1.12	Refraction Type	Record whether the subject's refraction category in both eyes is: 
 • Myopia with against-the-rule astigmatism (axis $90 \pm 30^\circ$) • Myopia with with-the-rule astigmatism (axis $180 \pm 30^\circ$) • Hyperopia with against-the-rule astigmatism (axis $90 \pm 30^\circ$) • Hyperopia with with-the-rule astigmatism (axis $180 \pm 30^\circ$) • None of the above
1.13	Biomicroscopy	FDA Slit Lamp Classification Scale will be used to grade the findings and determine eligibility. If any of these slit lamp findings are grade 3 or higher, the subject may not continue at this time, but may return up to one additional time to determine eligibility. If discontinued, a final examination must be completed (biomicroscopy does not need to be repeated).

Clinical Study Protocol
Johnson & Johnson Vision Care, Inc.

Visit 1: Baseline		
Step	Procedure	Details
		If the clearance of the fluorescein needs to be expedited, preservative-free rewetting drops may be instilled.
1.14	Eligibility at Baseline	
All responses to Inclusion Criteria questions must be answered “yes” and all responses to Exclusion Criteria questions must be answered “no” for the subject to be considered eligible.
 
If subject is deemed to be ineligible after baseline, proceed to Final Evaluation and complete all forms.

1.15	Instructions	
 • The subject is advised that the study contact lenses are a power that may not be a close match to their prescription, since the purpose of the study is to evaluate lens fit and comfort. • While wearing the study lenses, if the subject experiences blurry vision, they should remain seated in the exam chair. • If the subject experiences unacceptable headaches or nausea while wearing the study lenses, they should inform the study staff immediately and the lenses will be removed.

Visit 1: Treatment 1 Lens Fitting			
Step	Procedure	Details	
1.16	Randomization	Record the randomization ID	
1.17	Lens Selection	
Assign the study lens type based on the randomization scheme.
 
 • Myopes with against-the-rule astigmatism will wear -3.00/-1.00 x 90 or -3.00/-1.75 x 90 in each eye • Myopes with with-the-rule astigmatism will wear -3.00/-1.00 x 180 or -3.00/-1.75 x 180 in each eye • Hyperopes with against-the-rule astigmatism will wear +3.00/-1.00 x 90 or +3.00/-1.75 x 90 in each eye 	Appendix D

Clinical Study Protocol
Johnson & Johnson Vision Care, Inc.

Visit 1: Treatment 1 Lens Fitting		
Step	Procedure	Details
		
 Hyperopes with with-the-rule astigmatism will wear +3.00/-1.00 x 180 or +3.00/-1.75 x 180 in each eye 
Record the test lens parameters (power and lot number).

1.18	Right Lens Insertion	
Subjects will insert the right lens themselves. If the lens is uncomfortable, inspect for damage and remove, reinsert or replace as necessary.
 
Damaged lenses will be stored in a labeled vial with saline for shipment back to the Sponsor. Complete the Quality Product Complaint form.

1.19	Timed Settling for Right Lens	
The investigator will start a stopwatch as soon as the right lens is inserted.
 
Note: All lenses in this study have toric orientation marks at the 6 and 12 o'clock positions. Rotation measurements are made relative to a vertical reference line.
 
At one (1) minute after insertion, record:
 
 The direction of rotation as base nasal or base temporal. The magnitude of rotation error to the nearest degree. 
At three (3) minutes after insertion, record:
 
 The direction of rotation as base nasal or base temporal. The magnitude of rotation error to the nearest degree.
1.20	Left Lens Insertion	
Subjects will insert the left lens themselves. If the lens is uncomfortable, inspect for damage and remove, reinsert or replace as necessary.
 
Damaged lenses will be stored in a labeled vial with saline for shipment back to the Sponsor. Complete the Quality Product Complaint form.

1.21	Timed Settling for Left Lens	
The investigator will start a stopwatch as soon as the left lens is inserted.
 
Note: All lenses in this study have toric orientation marks at the 6 and 12 o'clock

Clinical Study Protocol
Johnson & Johnson Vision Care, Inc.

Visit 1: Treatment 1 Lens Fitting		
Step	Procedure	Details
		
positions. Rotation measurements are made relative to a vertical reference line.
 
At one (1) minute after insertion, record:
 
 • The direction of rotation as base nasal or base temporal. The magnitude of rotation error to the nearest degree. 
At three (3) minutes after insertion, record:
 
 • The direction of rotation as base nasal or base temporal. The magnitude of rotation error to the nearest degree.
1.22	Toric Fit Evaluation (7 minutes after insertion)	
At approximately 7 minutes after last lens insertion, record:
 
 • The direction of rotation as base nasal or base temporal. The magnitude of rotation error to the nearest degree. • Lens stability with blink • Toric fit acceptable or unacceptable 
Toric lens fit will be unacceptable if lenses are rotated more than 30 degrees, or lens stability is worse than 5 degrees movement with blink.
 
Unacceptable toric fit is not a reason to discontinue the subject.

1.23	Toric Fit Evaluation (15 minutes after insertion)	
At approximately 15 minutes after last lens insertion, record:
 
 • The direction of rotation as base nasal or base temporal. The magnitude of rotation error to the nearest degree. • Lens stability with blink • Toric fit acceptable or unacceptable 
Toric lens fit will be unacceptable if lenses are rotated more than 30 degrees, or lens stability is worse than 5 degrees movement with blink.
 
Unacceptable toric fit is not a reason to discontinue the subject.

1.24	Toric Fit Evaluation (25 minutes after insertion)	
At approximately 25 minutes after last lens insertion, record:
 
 • The direction of rotation as base nasal or base temporal. The magnitude of rotation error to the nearest degree. • Lens stability with blink

Clinical Study Protocol
Johnson & Johnson Vision Care, Inc.

Visit 1: Treatment 1 Lens Fitting		
Step	Procedure	Details
		
 • Toric fit acceptable or unacceptable 
Toric lens fit will be unacceptable if lenses are rotated more than 30 degrees, or lens stability is worse than 5 degrees movement with blink.
 
Unacceptable toric fit is not a reason to discontinue the subject.

1.25	Lens Fit Assessment	
Evaluate and grade lens centration, primary gaze movement, upgaze movement and tightness (push-up test).
 
The lens fit is unacceptable if any of the following is observed:
 
 • presence of limbal exposure (appearance of clear cornea) in any gaze • presence of edge lift • presence of unacceptable movement (excessive or insufficient) in all three movement categories (primary gaze, upgaze, and push-up). 
If either lens is deemed unacceptable, the subject will be discontinued from the study. Remove the lenses, perform a slit-lamp evaluation, and complete the Final Evaluation form.

1.26	PRO questionnaire	Approximately 30 to 40 minutes after last lens insertion, the subject will respond to the Post-Fit PRO (CLUE Comfort, Handling) Questionnaire.
1.27	Lens removal	The worn lenses may be discarded.
1.28	Biomicroscopy	
FDA Slit Lamp Classification Scale will be used to grade the findings and determine eligibility.
 
If the clearance of the fluorescein needs to be expedited, preservative-free rewetting drops may be instilled.

Clinical Study Protocol
Johnson & Johnson Vision Care, Inc.

Visit 1: Treatment 2 Lens Fitting			
Step	Procedure	Details	
1.29	Washout period	Allow at least 15 minutes break between removal of previous lenses and the insertion of next lens type.	
1.30	Lens Selection	
Assign the study lens type based on the randomization scheme.
 
 • Myopes with against-the-rule astigmatism will wear -3.00/-1.00 x 90 or -3.00/-1.75 x 90 in each eye • Myopes with with-the-rule astigmatism will wear -3.00/-1.00 x 180 or -3.00/-1.75 x 180 in each eye • Hyperopes with against-the-rule astigmatism will wear +3.00/-1.00 x 90 or +3.00/-1.75 x 90 in each eye • Hyperopes with with-the-rule astigmatism will wear +3.00/-1.00 x 180 or +3.00/-1.75 x 180 in each eye 
Record the test lens parameters (power and lot number).
	Appendix D
1.31	Right Lens Insertion	
Subjects will insert the right lens themselves. If the lens is uncomfortable, inspect for damage and remove, reinsert or replace as necessary.
 
Damaged lenses will be stored in a labeled vial with saline for shipment back to the Sponsor. Complete the Quality Product Complaint form.
	
1.32	Timed Settling for Right Lens	
The investigator will start a stopwatch as soon as the right lens is inserted.
 
Note: All lenses in this study have toric orientation marks at the 6 and 12 o'clock positions. Rotation measurements are made relative to a vertical reference line.
 
At one (1) minute after insertion, record:
 
 • The direction of rotation as base nasal or base temporal. The magnitude of rotation error to the nearest degree. 
At three (3) minutes after insertion, record:
	

Clinical Study Protocol
Johnson & Johnson Vision Care, Inc.

Visit 1: Treatment 2 Lens Fitting		
Step	Procedure	Details
		
 • The direction of rotation as base nasal or base temporal. The magnitude of rotation error to the nearest degree.
1.33	Left Lens Insertion	
Subjects will insert the left lens themselves. If the lens is uncomfortable, inspect for damage and remove, reinsert or replace as necessary.
 
Damaged lenses will be stored in a labeled vial with saline for shipment back to the Sponsor. Complete the Quality Product Complaint form.

1.34	Timed Settling for Left Lens	
The investigator will start a stopwatch as soon as the left lens is inserted.
 
Note: All lenses in this study have toric orientation marks at the 6 and 12 o'clock positions. Rotation measurements are made relative to a vertical reference line.
 
At one (1) minute after insertion, record:
 
 • The direction of rotation as base nasal or base temporal. The magnitude of rotation error to the nearest degree. 
At three (3) minutes after insertion, record:
 
 • The direction of rotation as base nasal or base temporal. The magnitude of rotation error to the nearest degree.
1.35	Toric Fit Evaluation (7 minutes after insertion)	
At approximately 7 minutes after last lens insertion, record:
 
 • The direction of rotation as base nasal or base temporal. The magnitude of rotation error to the nearest degree. • Lens stability with blink • Toric fit acceptable or unacceptable 
Toric lens fit will be unacceptable if lenses are rotated more than 30 degrees, or lens stability is worse than 5 degrees movement with blink.
 
Unacceptable toric fit is not a reason to discontinue the subject.

1.36	Toric Fit Evaluation (15 minutes after insertion)	
At approximately 15 minutes after last lens insertion, record:

Clinical Study Protocol
Johnson & Johnson Vision Care, Inc.

Visit 1: Treatment 2 Lens Fitting		
Step	Procedure	Details
		
 • The direction of rotation as base nasal or base temporal. The magnitude of rotation error to the nearest degree. • Lens stability with blink • Toric fit acceptable or unacceptable 
Toric lens fit will be unacceptable if lenses are rotated more than 30 degrees, or lens stability is worse than 5 degrees movement with blink.
 
Unacceptable toric fit is not a reason to discontinue the subject.

1.37	Toric Fit Evaluation (25 minutes after insertion)	
At approximately 25 minutes after last lens insertion, record:
 
 • The direction of rotation as base nasal or base temporal. The magnitude of rotation error to the nearest degree. • Lens stability with blink • Toric fit acceptable or unacceptable 
Toric lens fit will be unacceptable if lenses are rotated more than 30 degrees, or lens stability is worse than 5 degrees movement with blink.
 
Unacceptable toric fit is not a reason to discontinue the subject.

1.38	Lens Fit Assessment	
Evaluate and grade lens centration, primary gaze movement, upgaze movement and tightness (push-up test).
 
The lens fit is unacceptable if any of the following is observed:
 
 • presence of limbal exposure (appearance of clear cornea) in any gaze • presence of edge lift • presence of unacceptable movement (excessive or insufficient) in all three movement categories (primary gaze, upgaze, and push-up). 
If either lens is deemed unacceptable, the subject will be discontinued from the study. Remove the lenses, perform a slit-lamp evaluation, and complete the Final Evaluation form.

Clinical Study Protocol
Johnson & Johnson Vision Care, Inc.

Visit 1: Treatment 2 Lens Fitting		
Step	Procedure	Details
1.39	PRO questionnaire	Approximately 30 to 40 minutes after last lens insertion, the subject will respond to the Post-Fit PRO (CLUE Comfort) Questionnaire.
1.40	Lens removal	The worn lenses may be discarded.

FINAL EVALUATION

The final evaluation will ordinarily take place immediately following the last scheduled lens fitting per the study protocol. It may also take place at any point the subject discontinues the study or is terminated from the study.

Final Evaluation		
Step	Procedure	Details
F.1	Final Exam Form	Indicate if the subject completed the study successfully. If subject discontinued from the study, indicate the reason.
F.2	Biomicroscopy	FDA Slit Lamp Classification Scale will be used to grade the findings and determine eligibility. If the clearance of the fluorescein needs to be expedited, preservative-free rewetting drops or saline may be instilled.
F.3	Subjective spherocylindrical Refraction	An optimal, binocular balanced distance spherocylindrical refraction will be performed. Record the refraction and distance visual acuity (OD, OS, OU) to the nearest letter.
F.4	Exit Distance Visual Acuity	Record the distance Snellen visual acuity (OD, OS, OU) to the nearest letter with the subject's habitual distance spectacle correction in place.

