2. STUDY OBJECTIVES, ENDPOINTS AND HYPOTHESES

2.1. Objectives

Primary Objective:

The primary objective of this study is to evaluate absolute rotation of the investigational multifocal toric contact lens 15-minutes after insertion.

Clinical Study Protocol

Johnson & Johnson Vision Care, Inc.

Exploratory Objectives:

Exploratory objectives include evaluations of absolute rotation at 1-, 3-, 7- and, 25-minutes and rotational stability with blink at 15- and 25-minutes. Additionally, initial comfort and handling scores will be assessed.

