2.2. Endpoints

Primary endpoint:

Absolute rotation $\leq 10^\circ$ (Acceptable Absolute Rotation)

Absolute rotation will be assessed at 1-, 3-, 7-, 15- and 25-minutes after insertion for each subject eye. However, absolute rotation at 15-minutes will be the primary endpoint. Acceptable absolute rotation is a binary response where Y=1 if absolute rotation is less than or equal to 10° and Y=0 otherwise (absolute rotation greater than 10°). See [REDACTED] in Appendix D for additional details on the collection of absolute rotation.

Exploratory endpoints:

- Summary of Rotation 1-, 3-, 7- and, 25-minutes after insertion
- Rotational stability with blink 15- and 25-minutes after insertion
- Comfort scores approximately 30-minutes after insertion
- Handling scores approximately 30-minutes after insertion

Comfort and handling scores will be assessed using the Contact Lens User Experience (CLUE™) questionnaire approximately 30-minutes after lens insertion. CLUE™ is a validated patient-reported outcomes questionnaire to assess patient-experience attributes of soft, disposable contact lenses (comfort, vision, handling, and packaging) in a contact-lens wearing population in the US, ages 18-65. Derived CLUE™ scores using Item Response Theory (IRT) follow a normal distribution with a population average score of 60 (SD 20), where higher scores indicate a more favorable/positive response with a range of 0-120. A 5-point increase in an average CLUE™ score translates into 10% shift in the distribution of scores for population of soft contact lens.⁹

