14. STATISTICAL METHODS

14.1. General Considerations

Statistical Analysis will be undertaken by the sponsor or under the authority of the sponsor. A general description of the statistical methods to be implemented in this clinical trial is outlined below.

All data summaries and statistical analyses will be performed using the Statistical Analysis System (SAS) software Version 9.4 or higher (SAS Institute, Cary, NC).¹¹ Throughout the analysis of data, the results for each subject/eye will be used when available for summarization and statistical analysis. Unscheduled visits will be summarized.

Summary tables (descriptive statistics and/or frequency tables) will be provided for all baseline variables, efficacy variables and safety variables as appropriate. Continuous variables will be summarized with descriptive statistics (n, mean, standard deviation [SD], median, minimum and maximum). Frequency count and percentage of subjects or eyes within each category will be provided for categorical data. Summary tables will be summarized by timepoint, group and lens.

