14.7. Other Exploratory Analyses

Exploratory endpoints will be descriptively summarized.

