14.9. Procedure for Handling Missing Data and Drop-Outs

Missing or spurious values will not be imputed. The count of missing values will be included in the summary tables and listings.

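### Step 1.39 leaves handling out of the second-lens questionnaire, so the exploratory handling scores would come from period 1 only if it is followed as written

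*Combined protocol and SAP*

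**What the plan says.** The exploratory objectives in Section 2.1 state: "Additionally, initial comfort and handling scores will be assessed". Section 2.2 lists handling scores as an exploratory endpoint and gives the instrument and timing: "Comfort and handling scores will be assessed using the Contact Lens User Experience (CLUE™) questionnaire approximately 30-minutes after lens insertion". Neither section limits handling to one lens or one period. Section 4.1 also describes assessing comfort and handling in a design where each subject wears two lens types.

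The procedures in Section 7.2 differ between the two lenses:

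- Step 1.26, first lens: "the subject will respond to the Post-Fit PRO (CLUE Comfort, Handling) Questionnaire".
- Step 1.39, second lens: "the subject will respond to the Post-Fit PRO (CLUE Comfort) Questionnaire".

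Table 4 in Section 7.1 has a single PRO questionnaire row marked XX, with the key "Note: X = performed once, XX = performed twice". It does not list domains.

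On analysis, Section 14.1 says "Summary tables will be summarized by timepoint, group and lens", Section 14.7 says "Exploratory endpoints will be descriptively summarized", and Section 14.9 says "Missing or spurious values will not be imputed".

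**The concern.** The two questionnaire steps have the same timing and, apart from the domain list, the same wording. One names two domains and the other names one. Subjects insert both lenses themselves again in period 2 (steps 1.31 and 1.33), so there is a second handling experience to score, and nothing in the protocol explains why it should go unscored.

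The step text matters because it may drive the form. The synopsis says questionnaire responses are entered directly by computer, and Section 15.1 says the eCRFs are built to match the study procedures. If a period-2 form were built from step 1.39, handling would be missing for every subject at every site. With a single visit and no imputation, the scores could not be recovered afterwards.

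For this endpoint the crossover would in effect become a parallel comparison. Each subject would score one lens, the two cylinder powers would be scored by different people, and every score would come from the first wearing period.

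**Working it through.** **Comparison of the text**

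| Place | Comfort | Handling | Period limit |
|---|---|---|---|
| Sections 2.1, 2.2, 4.1 | yes | yes | none stated |
| Table 4, PRO row | domains not listed | domains not listed | performed twice |
| Step 1.26 (first lens) | yes | yes | – |
| Step 1.39 (second lens) | yes | not named | – |
| Other Treatment 2 steps; Final Evaluation F.1 to F.4 | no | no | – |

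Handling for the second lens is therefore implied by the endpoint sections and by Table 4, but no procedure step collects it. Both sentences in Section 7.2 are complete, so neither a redaction nor a broken table explains the difference.

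**Size of the effect if step 1.39 is followed literally**

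The plan gives no precision figure for handling, so there is none to reproduce.

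Inputs:

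- 80 completers, 40 myopes and 40 hyperopes (Section 4.1).
- Two lens types per subject (Section 4.1, Table 1).
- CLUE population SD of 20 (Section 2.2).
- Assumption: equal numbers in the two sequences. The ratio is not stated.
- Assumption, for the last row only: 20 completers in each of the four refraction groups. Section 4.3 aims only for at least 15 enrolled in each.

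Counts:

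- Handling at both lenses: 80 × 2 = 160 scores, 80 per cylinder power, all paired.
- Handling at the first lens only: 80 × 1 = 80 scores, 80 / 2 = 40 per cylinder power, none paired.

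Precision of a by-lens mean: SE = 20/√n and 95% half-width = 1.96 × SE.

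- n = 80: SE = 20/8.94 = 2.24, half-width 4.4.
- n = 40: SE = 20/6.32 = 3.16, half-width 6.2.
- n = 20: SE = 20/4.47 = 4.47, half-width 8.8.
- n = 10: SE = 20/3.16 = 6.32, half-width 12.4.

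Section 14.1 asks for summaries by group and lens but does not define group, so three levels are shown:

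| Level of summary | n per lens, both periods | n per lens, period 1 only | Half-width, both periods | Half-width, period 1 only |
|---|---|---|---|---|
| All subjects | 80 | 40 | 4.4 | 6.2 |
| Myopes or hyperopes | 40 | 20 | 6.2 | 8.8 |
| Four refraction groups | 20 | 10 | 8.8 | 12.4 |

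Halving n multiplies each SE by √2 = 1.41. For scale, the only benchmark in Section 2.2 is a 5-point change in the average CLUE score. Over all subjects the half-width lies just below that with full collection and above it with period 1 alone.

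**The case against.** The strongest reply is that no data may be lost at all. The Appendix A questionnaires are not shown. Both steps use the same name for the instrument, and Table 4 has one questionnaire row performed twice. That fits a single form given after each lens, with a word left out of one parenthesis. Section 15.1 speaks of forms matching the procedures for each visit. There is only one visit, and its procedures do include handling, so that sentence does not show that a separate comfort-only form exists. This stands: the mismatch in the text is certain, and the loss of data is conditional.

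The second reply is that the precision figures go beyond the plan. Handling has no hypothesis, planned interval, between-lens comparison or precision target; Section 14.1 lists only n, mean, SD, median, minimum and maximum. The SD of 20 is a population value for US wearers aged 18 to 65, not an estimate for astigmatic subjects aged 40 to 70 wearing powers that do not match their refraction. The sequence ratio and group sizes are assumed. This also stands, so the half-widths show scale only. The firm figure is the count: 80 of 160 scores.

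Third, randomized sequences would leave period-1 handling data on both cylinder powers, so by-lens summaries could still be produced. That is correct, but they would rest on half the scores, and no within-subject description would be possible.

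None of these replies removes the contradiction between the two steps.

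**Conclusion.** The point holds. Step 1.39 conflicts with step 1.26 and with the endpoint in Section 2.2, and nothing else in the procedures fills the gap. If sites and forms follow step 1.39 as written, half of the planned handling scores are never collected and the standard error of a by-lens mean is 1.41 times as large. That result is for 80 completers; the 40 per cylinder power also assumes equal sequences, and the standard errors in points assume the stated SD of 20.

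Confidence is high for the mismatch. Whether data would actually be lost cannot be settled from the documents. The consequence is confined to one exploratory, descriptive endpoint: the 15-minute rotation endpoint, its power and type I error, and safety are untouched. It is worth correcting because the loss would be systematic and could not be made good later.

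**What to change.** Add handling to the questionnaire named in step 1.39 so that it matches step 1.26, and confirm that the period-2 questionnaire form contains the handling items. If handling is meant to be scored for the first lens only, say so in Sections 2.1 and 2.2 and in Table 4, and give the reason.

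The cost is one word in the protocol and one check of the form. If the period-2 form does lack the items, adding them takes perhaps a minute or two of each subject's time.
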